10.3. INTERIM ANALYSIS AND DATA MONITORING

An Independent Data Monitoring Committee will meet approximately every 6 months to review accrual, safety and efficacy data. The subsequent replacement of patients who withdraw from treatment or who are unevaluable for reasons deemed not to be treatment related will be based on the advice of this committee. For completeness a sensitivity analysis of the progression free rate calculated by the Kaplan Meier product limit method will also be presented in which withdrawals are censored.

A formal interim analysis will be conducted once the first 37 patients have at least 6 months follow up data available. The principal analysis for publication will occur on the recommendation of the IDMSC and is expected once 99 patients have at least 6 months follow up data available (or have died).

11. TRIAL MANAGEMENT

11.1. TRIAL MANAGEMENT GROUP (TMG)

A Trial Management Group (TMG) will be set up and will include the Chief Investigator, Co-investigators and identified collaborators, the Trial Statistician and the Trial Managers. Principal Investigators and key study personnel will be invited to join the TMG as appropriate to ensure representation from a range of centres and professional groups. Where possible, membership will include a lay/consumer representative. Notwithstanding the legal obligations of the Co-Sponsors and Chief Investigator, the TMG have operational responsibility for the conduct of the trial. The Committee's terms of reference, roles and responsibilities will be defined in a charter issued by ICR-CTSU and based on MRC Good Clinical Practice (MRC GCP). Use of biological samples or study data for purposes additional to those described within the protocol must be approved by the A-PREDICT Trial Management Group.

11.2. INDEPENDENT DATA MONITORING AND STEERING COMMITTEE (IDMSC)

The roles of the IDMC and TSC will be combined, i.e. the committee will both monitor the data produced by the trial, put these data into overall context and supervise the progress of the trial towards its interim and overall objectives. This committee will be constituted according to MRC Good Clinical Practice (MRC GCP) and will oversee the safety of the trial.

The IDMSc will meet in confidence at regular intervals, and at least annually. A report of the findings and recommendations will be produced following each meeting. This report will be submitted to the TMG and if required, the main REC and the MHRA.

The IDMSc reserve the right to release any data on outcome or side-effects to the TMG (and if appropriate to participants) if it determines at any stage that the combined evidence from this and other studies justifies it.

The Committee's terms of reference, roles and responsibilities will be defined in a charter issued by ICR-CTSU.

12. RESEARCH GOVERNANCE

This Clinical Trial will be conducted in accordance with the ethical principles laid down by the Declaration of Helsinki, 1964 and as amended in 1996 and the principles of Good Clinical Practice.

12.1. SPONSOR RESPONSIBILITIES

The Co-sponsors are The Institute of Cancer Research (ICR) and The Royal Marsden NHS Foundation Trust (RMH). Sponsorship activities and delegated responsibilities are shared between ICR and RMH, in accordance with The Medicines for Human Use (Clinical Trials) Regulations 2004 as amended and in line with the Research Governance Framework for Health and Social Care and the principles of GCP. Responsibilities of the Co-sponsors are set out in an agreement between ICR and RMH.

12.2. PRINCIPAL INVESTIGATOR RESPONSIBILITIES

Responsibilities of each Principal Investigator and participating centre will be detailed in a contract with the Co-sponsors.

Principal Investigator responsibilities include putting and keeping in place arrangements to run the trial at their site according to the trial protocol and applicable guidance notes, The Medicines for Human Use (Clinical Trials) Regulations 2004 as amended and in line with the Research Governance Framework for Health and Social Care and the principles of GCP. The above responsibilities include, but are not limited to, the following:

- Putting and keeping in place arrangements to adhere the principles of GCP
- Keeping a copy of all 'essential documents' (as defined under the principles of GCP) and ensuring appropriate archiving and destruction of documentation once the trial has ended as required by regulation 31 of the principal Regulations of the Medicines for Human Use (Clinical Trials) Regulations 2004 implementing the commission directive 2005/28EC
- Ensuring investigational medicinal products (IMPs) are made available to subjects free of charge
- Taking appropriate urgent safety measures and
- Ensuring recording and prompt reporting of SAEs/SARs to ICR-CTSU

ICR is responsible for co-ordinating any required legal agreements and investigator statements.

The delegation of sponsorship responsibilities does not impact on or alter standard NHS indemnity cover. The agreement of delegated responsibilities is viewed as a partnership and as such it is necessary to share pertinent information between ICR and RMH/Chief Investigator, including proposed inspections by the MHRA and/or other regulatory bodies.

12.3. PFIZER RESPONSIBILITIES

Pfizer are responsible on behalf of the co-sponsors for the manufacture, packing, labelling and distributing of study drug to site in accordance with Good Manufacturing Practice and all applicable local legislation. Responsibilities are defined in an agreement between Pfizer and the co-sponsors.

13. TRIAL ADMINISTRATION & LOGISTICS

13.1. SITE ACTIVATION

Before activating the trial, participating centres are required to sign an agreement accepting responsibility for all trial activity which takes place within their centre.

Sites may commence recruitment once centre agreements have been signed by both parties, trial documentation is in place and a site initiation (visit or teleconference) has taken place. Site initiation visits will be conducted at sites where the Principal Investigator has requested one or where ICR-CTSU deems it is appropriate.

13.2. DATA ACQUISITION

Electronic (e) Case Report Forms (CRF) will be used for the collection of trial data. ICR-CTSU will provide guidance to sites to aid the completion of the eCRFs. The Trial Management Group reserves the right to amend or add to the eCRF template as appropriate. Such changes do not constitute a protocol amendment, and revised or additional forms should be used by centres in accordance with the guidelines provided by ICR-CTSU.

By participating in the A-PREDICT trial, the Principal Investigators at each centre are confirming agreement with his/her local NHS Trust to ensure that:

- Sufficient data is recorded for all participating patients to enable accurate linkage between hospital records and eCRFs;
- Source data and all trial related documentation are accurate, complete, maintained and accessible for monitoring and audit visits;
- All staff at their centre who are involved with the trial will meet the requirements of the EU Directive;
- Original consent forms are dated and signed by both patient and investigator and are kept together in a central log together with a copy of the specific patient information sheet(s) given at the time of consent;
- All essential documents must be retained for five years after the Trial ends to comply with current legislation.
- Staff will comply with the protocol and Trial Guidance Notes for the A-PREDICT trial.

13.3. CENTRAL DATA MONITORING

Once data has been entered by the site personnel on the eCRF, ICR-CTSU will review it for compliance with the protocol, and for inconsistent or missing data. Should any missing data or data anomalies be found, queries will be issued to the centre for resolution.

Any systematic inconsistencies identified may trigger monitoring visits to centres.

13.4. ON-SITE MONITORING

If a monitoring visit is required, ICR-CTSU will contact the centre to discuss dates of proposed visit. Once a date has been confirmed, the centre should ensure that the relevant patient notes are available for monitoring.

ICR-CTSU and/or Francis Crick Institute staff conducting on-site monitoring will review essential documentation, carry out source data verification and monitor pharmacy and translational study procedures to confirm compliance with the site agreement and trial protocol to ensure the protection of patients' rights as detailed in the Declaration of Helsinki 1964 as amended October 1996.

If any problems are detected during the course of the monitoring visit, ICR-CTSU will work with the Principal Investigator or delegated individual to resolve issues and determine appropriate action.

13.5. COMPLETION OF THE STUDY AND DEFINITION OF STUDY END DATE

The study end date is deemed to be the date of last data capture.

13.6. ARCHIVING

Essential documents are documents that individually and collectively permit evaluation of the conduct of the trial and substantiate the quality of the data collected. They should be retained for a sufficient period (and at least 5 years after the date of last data capture) for possible inspection by the regulatory authorities. Documents should be securely stored and access restricted to authorised personnel.

14. PATIENT PROTECTION AND ETHICAL CONSIDERATIONS

This trial has been formally assessed for clinical risk by ICR-CTSU.

The trial has received ethical and regulatory approval. Before entering patients, the Principal Investigator at each site is responsible for submitting Site Specific Information and gaining local Research and Development approval of this protocol.

Patients should be asked to sign the trial consent forms at trial entry after receiving both verbal and written information about the trial. All consent forms must be countersigned by the Principal Investigator or a designated individual. A Delegation of Responsibilities Log, listing the designated individuals and the circumstances under which they may countersign consent forms, must be maintained at the participating centre. This log, together with original copies of all signed patient consent forms, should be retained in the Site Investigator File and must be available for inspection. The A-PREDICT patient information sheets should be provided in addition to any standard patient information sheets that are provided by the centre and used in routine practice.

14.1. PATIENT CONFIDENTIALITY

Patients will be asked to consent to their full name being collected at registration in addition to their date of birth, hospital number, postcode and NHS number (CHI in Scotland) to allow linkage with routinely collected NHS data and ensure accuracy in handling biological samples. The personal data recorded on all documents will be regarded as confidential, and any information which would allow individual patients to be identified will not be released into the public domain.

Each investigator should keep a separate log of all patients' Trial IDs, names, addresses and hospital numbers. The investigator must maintain trial documents, which are to be held at the participating centres (e.g. patients' written consent forms), in strict confidence. The investigator must ensure the patients' confidentiality is maintained at all times.

ICR-CTSU will maintain the confidentiality of patients at all times and will not reproduce or disclose any information by which patients could be identified. Representatives of ICR-CTSU and the regulatory authorities will be required to have access to patients notes for quality assurance purposes but patients should be reassured that their confidentiality will be respected at all times.

14.2. DATA PROTECTION ACT (DPA)

ICR-CTSU will comply with all aspects of the DPA 1998. Any requests from patients for access to data about them held at ICR-CTSU will be referred to the Data Protection Officer at The Institute of Cancer Research.

14.3. LIABILITY

Indemnity for participating hospitals is provided by the usual NHS indemnity arrangements.

15. FINANCIAL MATTERS

The trial is investigator designed and led and has been endorsed by Clinical Trials Awards & Advisory Committee (CTAAC) of Cancer Research UK, and meets the criteria for R&D support as outlined in the Statement of Partnership on Non-Commercial R&D in the NHS in England.

The trial has received an Investigator Initiated Research grant (IIR) from Pfizer. If further funding is received from any other source this will be made apparent in the patient information sheet and to the approving Main REC, but will not require a protocol amendment.

NCRN (or regional equivalent) network resources should be made available for A-PREDICT, as the trial is part of the NIHR portfolio by virtue of its endorsement by CTAAC.

16. PUBLICATION POLICY

The main trial results will be published in a peer-reviewed journal, on behalf of all collaborators. The manuscript will be prepared by a writing group, consisting of members of the Trial Management Group, and participating clinicians. All participating clinicians will be acknowledged in the publication. All presentations and publications relating to the trial must be authorised by the Trial Management Group. Authorship of any secondary publications e.g. relating to the various biological studies will reflect the intellectual and time input into these studies, and will not be the same as on the primary publication. No investigator may present or attempt to publish data relating to the A-PREDICT trial without prior permission from the Trial Management Group.

18. APPENDIX A: RECIST

Response Evaluation Criteria in Solid Tumours (RECIST) Version 1.1 criteria should be used for the assessment of treatment outcomes.

18.1. EVALUATION OF MEASURABLE AND NON-MEASURABLE LESIONS

- **Measurable disease** – the presence of at least one measurable lesion. If the measurable disease is restricted to a solitary lesion, its neoplastic nature should be confirmed by cytology / histology.
- **Measurable lesions** – lesions that can be accurately measured in at least one dimension with the longest diameter ≥ 20 mm by chest X-ray, or ≥ 10 mm by CT/MRI scan or clinical exam.
- Lytic bone lesions or mixed lytic-blastic lesions, with identifiable soft tissue components, that can be evaluated by cross sectional imaging techniques such as CT or MRI can be considered as measurable lesions if the soft tissue component meets the definition of measurability described above.
- ‘Cystic lesions’ thought to represent cystic metastases can be considered as measurable lesions, if they meet the definition of measurability described above. However, if non-cystic lesions are present in the same patient, these are preferred for selection as target lesions.
- Malignant lymph nodes must be ≥ 15 mm in the short axis when assessed by CT scan to be considered measurable.
- **Non-measurable lesions** – all other lesions, including small lesions and malignant lymph nodes (longest diameter <10 mm, or pathological lymph nodes with ≥ 10 to <15 mm short axis) i.e., leptomeningeal disease, ascites, pleural/pericardial effusion, inflammatory breast disease, lymphangitis cutis/pulmonis, cystic lesions, blastic bone lesions and also abdominal masses that are not confirmed and followed by imaging techniques.
- Tumour lesions situated in a previously irradiated area, or in an area subjected to other loco-regional therapy, are usually not considered measurable unless there has been demonstrated progression in the lesion.
- The utilisation of endoscopy and laparoscopy for objective tumour evaluation is not advised. The utilisation of such techniques should be restricted to confirming complete pathological response when biopsies are obtained.

18.2. BASELINE DOCUMENTATION OF TARGET AND NON-TARGET LESIONS

- Measurable lesions up to a maximum of 2 lesions per organ and 5 lesions in total representative of all involved organs should be identified as target lesions and recorded and measured at baseline.
- Target lesions should be selected on the basis of their size (lesions with the longest diameter), be representative of all involved organs, but in addition should be those that lend themselves to reproducible repeated measurements. It may be the case that, on occasion, the largest

lesion does not lend itself to reproducible measurement in which circumstance the next largest lesion which can be measured reproducibly should be selected.

- All measurements should be taken and recorded in metric notation, using a ruler or calipers. All screening evaluations should be performed as closely as possible to the beginning of treatment and never more than 4 weeks before the beginning of treatment.
- The same method of assessment and the same technique should be used to characterise each identified and reported lesion at baseline and during follow up.
- A sum of the longest diameters (LD) for all target lesions will be calculated and reported as the baseline sum of LD. The baseline sum LD will be used as reference by which to characterise the objective tumour.
- All other lesions (or sites of disease) should be identified as non-target lesions and should also be recorded at baseline. Measurements of these lesions are not required, but the presence or absence of each should be noted throughout follow up. In addition, it is possible to record multiple non-target lesions involving the same organ as a single item on the case record form (e.g. 'multiple enlarged pelvic lymph nodes' or 'multiple liver metastases').

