18.4. EVALUATION OF TARGET LESIONS

Response criteria	Evaluation of target lesions
Complete Response (CR)	Disappearance of all target lesions (lymph nodes must be <10mm short axis)
Partial Response (PR)	At least 30% decrease in the sum of LD of target lesions, taking as reference the baseline sum of LD.
Progressive Disease (PD)	At least 20% increase in the sum of LD of target lesions, taking as reference the smallest sum LD recorded since the treatment started and at least 5mm absolute increase in this sum or the appearance of one or more new lesions.
Stable Disease (SD)	Neither sufficient shrinkage to qualify for PR nor sufficient increase to qualify for PD, taking as reference the smallest sum LD since the treatment started.

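### Appendix A judges nodal target lesions by short axis for measurability and complete response, but by longest diameter for partial response, stable disease and progression

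*Combined protocol and SAP*

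**What the plan says.** Section 18 makes RECIST 1.1 the standard: "Response Evaluation Criteria in Solid Tumours (RECIST) Version 1.1 criteria should be used for the assessment of treatment outcomes". Appendix A then writes out the working rules.

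- **Measurability (18.1):** "Malignant lymph nodes must be ≥ 15 mm in the short axis when assessed by CT scan to be considered measurable".
- **Baseline sum (18.2):** "A sum of the longest diameters (LD) for all target lesions will be calculated". Nodes are not treated separately.
- **CR of target lesions (18.4):** "Disappearance of all target lesions (lymph nodes must be <10mm short axis".
- **PR (18.4):** "At least 30% decrease in the sum of LD of target lesions, taking as reference the baseline sum of LD".
- **PD (18.4):** "At least 20% increase in the sum of LD of target lesions, taking as reference the smallest sum LD recorded since the treatment started", together with an absolute rise of at least 5 mm in the sum, or a new lesion.
- **SD (18.4):** neither PR nor PD. The wording does not exclude a patient who meets CR.

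Section 18.3.2 confirms that nodes can be target lesions. Nowhere does Appendix A say that a node's short axis enters the sum. These categories feed the primary endpoint and PFS (sections 4.1, 10.2.1 and 10.2.2) and best overall response (sections 10.2.2 and 18.10). Sections 10.2.1 and 18.11 plan a blinded central review of the scans.

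**The concern.** A node becomes a target and is declared resolved on one axis, but its shrinkage and growth in between are tracked on the other. The two axes of a node need not change in proportion, so two things can follow.

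First, one scan can satisfy the CR rule for nodes and the SD wording for the sum. The overall-response table in 18.6 takes the target category as an input and so cannot settle which applies. Best overall response is exposed to this.

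Second, whether nodal growth counts as PD on the target sum can depend on the axis. PD is one of the two events in the primary endpoint, so the six-month status of a patient with predominantly nodal targets could change. Site and central readers might also differ: one may follow Appendix A literally, another whatever convention they take RECIST 1.1 to mean. Discordance at central review would then reflect the rule rather than the scan.

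**Working it through.** The plan gives no figure for nodal measurement, so there is none to reproduce. The check applies the 18.4 rules to assumed node sizes, written as short axis x longest diameter in mm. The sizes are illustrations; only the thresholds come from the documents (15 mm, 10 mm, -30%, +20% with +5 mm).

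Formulas: response change = (current sum - baseline sum) / baseline sum. Progression change = (current sum - nadir sum) / nadir sum, with the absolute difference alongside.

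**A. Shrinking node, sole target, 15x24 to 9x20.**
- Nodal CR rule: 9 mm is below 10 mm, so CR.
- Sum of longest diameters: (20 - 24)/24 = -16.7%. This is neither PR nor PD, so it fits SD.
- Both labels are progression free.

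**B. The same node regrows, 9x20 to 16x23.**
- By 18.1 it is measurable again (16 mm is at least 15 mm).
- Longest diameter from nadir: (23 - 20)/20 = +15.0%, +3 mm. Not PD.
- Short axis: (16 - 9)/9 = +77.8%, +7 mm. This would be PD if the short axis were summed.

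**C. The reverse direction, 18x24 to 19x30.**
- Longest diameter: (30 - 24)/24 = +25.0%, +6 mm. PD.
- Short axis: (19 - 18)/18 = +5.6%, +1 mm. Not PD.

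**D. Mixed patient: stable 20 mm non-nodal lesion plus node 16x30 to 24x33.**
- Longest diameters: (53 - 50)/50 = +6.0%, +3 mm. Not PD.
- Short axis for the node: (44 - 36)/36 = +22.2%, +8 mm. This would be PD.

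**Adding a measurable renal primary.** The documents give no primary size; assume a stable primary of P = 20 to 100 mm in the sum.

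| Case | Sum with node longest diameter, P = 20 to 100 | Sum with node short axis, P = 20 to 100 | Axis matters? |
|---|---|---|---|
| Node growing 15x24 to 20x26 | 2/(24+P): +4.5% to +1.6% | 5/(15+P): +14.3% to +4.3% | No |
| B | 3/(20+P): +7.5% to +2.5% | 7/(9+P): +24.1% to +6.4% | Only if P is 26 mm or less |
| C | 6/(24+P): +13.6% to +4.8% | 1/(18+P): +2.6% to +0.8% | No |
| D plus primary | 3/(50+P): +4.3% to +2.0% | 8/(36+P): +14.3% to +5.9% | No |

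For B, 7/(9+P) reaches 20% when 9+P is at most 35, hence P at most 26 mm. With a primary among the targets, target CR would also require that primary to disappear, so the double label in A would not arise on the node alone.

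**The case against.** Several counter-arguments have force.

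- **The CR/SD overlap cannot move the primary endpoint.** This stands; the overlap bears on best overall response only.
- **The response table is naturally read from the top, so CR wins.** That is sensible: an ordinary non-nodal CR also meets the literal PR rule and nobody would report both. But the order is not stated, and stating it would not settle the PD question.
- **Most patients here should have a renal primary in the sum.** Section 18.2 asks for targets representative of all involved organs, and section 7.1.1 requires a biopsy of the primary. This largely stands, as the table shows. Exceptions remain: an unmeasurable primary, larger nodal growth, or the new baseline after nephrectomy in section 7.10.
- **Longest diameter for baseline, nadir, PR and PD is one consistent measure, and the documents never define PD by short axis.** This is fair, so it is better to say that PD differs by axis than that progression is missed. Case B still shows a node crossing from Appendix A's own resolved threshold to its measurable threshold without PD on the sum.
- **Other safeguards exist.** RECIST 1.1 is the named standard, central review is planned, and new lesions or non-target progression also count as PD. These limit the harm but do not tell a reader which axis to sum.

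A reader might infer that the false-pass risk is inflated. The two-stage rule (11 of 37, then 32 of 99) has a pass probability of 4.9% at a true rate of 25%. Adding one, two or three wrongly progression-free patients per 99, that is using 0.25 + m/99, gives 7.8%, 11.6% or 16.4%. The documents do not support that reading. The count is arbitrary, and case C shows that the error can run the other way, where the same formula gives 3.0%, 1.7% or 0.9%.

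**Conclusion.** The inconsistency is real and follows from Appendix A's own wording. Its reach is limited.

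- **Best overall response:** a patient whose only targets are nodes can meet CR and the SD wording on one scan, with no stated precedence.
- **Primary endpoint and PFS:** where nodes dominate the target sum, PD can differ by axis in either direction. Some patients' status could change, with unknown frequency and no fixed direction of bias.
- **Patients with a measurable primary in the sum:** often no effect. In the illustrations only the regrowth case still differed, and only with a primary of 26 mm or less.

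This rests on assumed node and primary sizes and a primary that stays stable. The number of patients with nodal targets is not in the documents, so no shift in the six-month rate, type I error or power can be claimed. The sample size is unaffected.

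**What to change.** In sections 18.2 and 18.4, replace the sum of longest diameters with one sum of diameters: longest diameter for non-nodal targets and short axis for nodal targets. Short axis is the natural choice because Appendix A already uses it for nodal measurability and CR. Use this sum for baseline, nadir, PR, SD and PD. State that CR takes precedence over SD. Give site readers and the blinded central review the same written rule.

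The cost is wording in the appendix and a label on the tumour-assessment eCRF. No extra scan or measurement is needed, because the short axis is already required to qualify a node and to call it resolved.
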